### **11.3 Site monitoring**

Before study initiation, at a site initiation visit or at an investigator's meeting, a Novartis representative will review the protocol and data capture requirements (i.e., eSource DDE or eCRFs) with the investigators and their staff. During the study, Novartis employs several methods of ensuring protocol and GCP compliance and the quality/integrity of the sites' data. The field monitor will visit the site to check the completeness of patient records, the accuracy of data capture / data entry, the adherence to the protocol and to Good Clinical Practice (GCP), the progress of enrollment, and to ensure that study treatment is being stored, dispensed, and accounted for according to specifications. Key study personnel must be available to assist the field monitor during these visits. Continuous remote monitoring of each site's data may be performed by a centralized Novartis CRA organization. Additionally, a central analytics organization may analyze data & identify risks & trends for site operational parameters, and provide reports to Novartis/sponsor clinical teams to assist with trial oversight.

The investigator must maintain source documents for each patient in the study, consisting of case and visit notes (hospital or clinic medical records) containing demographic and medical information, laboratory data, ECGs, and the results of any other tests or assessments. All information on CRFs must be traceable to these source documents in the patient's file. The investigator must also keep the original informed consent form signed by the patient (a signed copy is given to the patient).

The investigator must give the monitor access to all relevant source documents to confirm their consistency with the data capture and/or data entry. Novartis monitoring standards require full verification for the presence of informed consent, adherence to the inclusion/exclusion criteria, documentation of SAEs, and of data that will be used for all primary variables. Additional checks of the consistency of the source data with the CRFs are performed according to the study-specific monitoring plan. No information in source documents about the identity of the patient will be disclosed.

## 12 Data analysis and statistical methods

Any data analysis carried out independently by the investigator should be submitted to Novartis before publication or presentation.

The dose level of KAF156 and LUM-SDF in the Run-in Cohort (12 to <18 years) may be adjusted after the first 24 patients have been dosed in this cohorts. Once the dose level has been adjusted, it becomes a different treatment group. The KAF156/LUM-SDF based treatment group will be labeled to include both the full dose level of the study drugs and food intake designation for KAF156 and LUM-SDF combination based treatment group (such as KAF156 400 mg & LUM-SDF 240 mg QDx2 with food, etc.). Since the the Run-in Cohort has different treatment groups (i.e. fed vs fasting) from Cohorts 1 and 2 (KAF156/LUM-DSF vs Coartem®), the Run-in Cohort will be analyzed separately from Cohorts 1 and 2. Statistical analysis will in general include Cohorts 1 and 2 pooled in addition to each cohort separately. In case that Cohort 2 stops early, such as after the first 24 patients, the study objectives will be assessed based on Cohort 1 data alone.

### 12.1 Analysis sets

The Randomized Analysis Set (RAS) consists of all randomized patients.

The Full Analysis Set (FAS) comprises all patients to whom study treatment has been assigned by randomization and who are treated with at least one dose of study drug with baseline *P. falciparum* asexual parasite count >0. According to the intent to treat principle, patients will be analyzed according to the treatment they have been assigned to during the randomization procedure.

The Safety Set includes all patients who received at least one dose of study treatment. Patients will be analyzed according to the study treatment received, where treatment received is defined as the randomized treatment if the patient took at least one dose of that treatment or the first treatment received if the randomized treatment was never received.

The Per-Protocol Set (PPS) is a subset of patients of the Full Analysis Set and is characterized by the following criteria:

- did not have important protocol deviations affecting efficacy,
- took at least 80% of study medication,
- did not take non-study drug antimalarial medications prior to Day 29 unless experiencing a treatment failure (ETF, LCF, LPF), and
- PCR corrected ACPR status at Day 29 can be defined

Important protocol deviations for exclusion from the PPS will be identified by the clinical team before database lock.

The PK set is a subset of the Full Analysis Set who had evaluable PK parameter/concentration data and took at least 80% of study medication.

## **12.2 Patient demographics and other baseline characteristics**

Demographic and other baseline data including disease characteristics will be listed and summarized descriptively by cohort and treatment group for the FAS and Safety set if Safety set is different from the FAS.

Categorical data will be presented as frequencies and percentages. For continuous data, mean, standard deviation (SD), median, minimum, and maximum will be presented. For selected parameters, 25th and 75th percentiles will also be presented.

Relevant medical histories and current medical conditions at baseline will be summarized by system organ class and preferred term, by cohort and treatment group.

## **12.3 Treatments**

The Safety set will be used for the analyses below. Categorical data will be summarized as frequencies and percentages by cohort and treatment group. For continuous data, mean, standard deviation, median, 25th and 75th percentiles, minimum, and maximum will be presented.

The duration of exposure in number of doses to KAF156, LUM-SDF, and Coartem® will be summarized by means of descriptive statistics. Percentage of patients with study drug vomiting and dose replacement will be presented. Average daily dosage and total dosage (in mg) of each drug (KAF156, LUM-SDF, and Coartem®) will be summarized. Meal intake and meal type will be summarized by day.

Concomitant medications and significant non-drug therapies prior to and after the start of the study treatment will be listed and summarized according to the Anatomical Therapeutic Chemical (ATC) classification system, by cohort and treatment group. Concomitant rescue and other anti-malarial medications will be summarized.

## **12.4 Analysis of the primary endpoint(s)**

[figure not shown]
### **12.4.1 Definition of primary endpoint(s)**

The primary efficacy variable is the PCR corrected Adequate Clinical and Parasitological Response (ACPR) at Day 29 (Cohorts 1 and 2 pooled).

In case that Cohort 2 stops early, such as after the first 24 patients, the study objectives will be assessed based on Cohort 1 data alone.

A patient is considered as PCR-corrected ACPR at Day 29 if the patient does not meet any of the criteria of ETF (up to Day 4), LCF (Day 5 to Day 29) or LPF (Day 8 to Day 29), and is absence of parasitaemia on Day 29 irrespective of axillary temperature unless the presence of parasitaemia after 7 days (Day 8 or later) is due to reinfection based on PCR genotyping.

A presence of parasitaemia after 7 days of treatment initiation is considered as a reinfection only if the parasitaemia is clear before Day 8 and none of the parasite strain(s) detected on Day 8 or later match with the parasite strain at baseline based on PCR genotyping.

Treatment failures after 7 days due to reinfection based on PCR genotyping are not considered as failure for PCR-corrected analyses but will be considered as failure for PCR uncorrected analyses.

#### 12.4.2 Statistical model, hypothesis, and method of analysis

The primary objective is to demonstrate the non-inferiority (NI) of a KAF156 and LUM-SDF combination to Coartem® for treatment of uncomplicated malaria caused by *P. falciparum* in children 6 months to < 12 years old. The NI margin ( $\Delta$ ) has been set to 10%.

The statistical null hypothesis is that the difference in PCR-corrected ACPR rate at Day 29 between KAF156 and LUM-SDF combination and Coartem® is at most -10% with the alternative hypothesis that it is greater than -10%. The statistical hypothesis will be evaluated using the lower limit of two-sided confidence interval for the difference between two treatment groups.

If Cohort 2 does not stop early, two-sided 95% CI for the difference between two treatment groups will be provided for Cohorts 1 and 2 pooled using Mantel-Haenszel estimate of the common risk difference stratified by cohort (see [SAS manual version 13.2 Pages 2681-2682, 2014](#)). If the lower limit of 2-sided 95% CI for the difference is greater than -10%, the null hypothesis will be rejected.

In case that Cohort 2 stops early, such as after the first 24 patients, two-sided 95% CI for the difference between two treatment groups will be provided for Cohort 1 alone using the Wilson uncorrected method. If the lower limit of 2-sided 95% CI for the difference is greater than -10%, the null hypothesis will be rejected.

[figure not shown]
The statistical hypothesis testing will be evaluated based on the PPS.

#### 12.4.3 Handling of missing values/censoring/discontinuations

No missing data are expected for the primary efficacy analysis based on PPS since patients who are not evaluable for the primary efficacy variable are excluded from PPS. See [Section 12.4.4](#) for missing data handling for the supportive analysis using FAS.

#### 12.4.4 Sensitivity analyses

- For patients who have a reinfection after 7 days but prior to Day 29 visit, such as at Day 15, the statistical method specified in [Section 12.4.2](#) will be performed by assigning treatment failure to these patients.
- The primary efficacy variable will be performed based on the FAS using the statistical method specified in [Section 12.4.2](#). Missing primary efficacy variable will be handled as follows:
  - Patients who received rescue medication for the treatment of *P. falciparum* malaria (except for the treatment of a new infection) will be considered treatment failures (from the day of rescue use onwards).
  - Patients who received other concomitant medication having an effect on malaria for reasons other than rescue therapy e.g. for the treatment of *P. vivax* [REDACTED]

(e.g., primaquine, certain antibiotics (sulfonamides, tetracycline, etc.)) will be considered in the analysis as if they had not taken the drug.

- Patients will be counted as failure if (a) they did not have a parasite count assessment at Day 29 unless these patients could be classified as cured based on absence of parasitemia at later time, or (b) they did not have valid PCR evaluations at baseline and Day 29 if parasitemia was present at Day 29.
- In addition, for the FAS, the proportion of patients with PCR-corrected ACPR at Day 29 and 95% CI by treatment group and the difference will be also estimated using the Kaplan-Meier method (Stepniewska and White 2006 and WHO 2015) which uses treatment failure as the event and treats missing data as censored instead of treatment failure. The PCR-corrected ACPR rate at Day 29 is estimated by the survival function at Day 29. Patients who had a new infection (i.e., reinfection) with *P. falciparum* or other species without *P. falciparum* recrudescence on or after Day 8 will be censored at the time of the first PCR that indicate the infection; patients who took antimalarial medications for reinfection or reasons other than rescue medication given for signs and symptoms of infection with *P. falciparum* or unsatisfactory therapeutic effect will be censored at the first time of such antimalarial medications; other patients without treatment failure will be censored at the time of the last parasitemia assessment. A two-sided 95% CI for the difference in proportion between the 2 treatment groups will be calculated based on the variance of individual proportion using the Greenwood formula.

Patients tested positive to COVID19 after Day 29 parasite assessment or after *P. falciparum* re-appearance (recrudescence or new infection) are included in the primary analysis and the sensitivity analyses similarly to other patients. Patients tested positive to COVID19 prior to Day 29 parasite assessment without *P. falciparum* re-appearance are handled similarly to other patients with missing Day 29 parasite assessment (e.g., loss to follow-up), i.e., excluded from PP set but included in FAS. If there are significant number of patients tested positive to COVID19 prior to Day 29 parasite assessment without *P. falciparum* re-appearance, additional sensitivity analyses may be considered.

## 12.5 Analysis of secondary endpoints

### 12.5.1 Efficacy and/or Pharmacodynamic endpoint(s)

**Secondary efficacy variables include:**

- PCR-corrected ACPR at Days 15 and 43;
- PCR-corrected ACPR at Day 29 for the Run-in Cohort, Cohort 1, and Cohort 2 separately;
- Uncorrected ACPR at Days 15, 29, and 43;
- Time to parasite clearance (PCT), defined as time from the first dose until the first total and continued disappearance of asexual parasite forms which remained at least a further 48 hours;
- Time to fever clearance (FCT), defined as time from the first dose until the first time the body temperature decreased below and remained below 37.5°C axillary or 38.0°C oral/tympanic/rectal for at least a further 24 hours;
- Proportion of patients with ETF:

- Proportion of patients with LCF;
- Proportion of patients with LPF;
- Incidence rate of recrudescence and reinfection at Days 15, 29 and 43.

Analyses of ACPRs (PCR corrected or uncorrected) will be based on the FAS and PPS. Analyses of other secondary efficacy variables will be based on the FAS. Analyses will be performed by cohort and for Cohorts 1 and 2 pooled. Note: difference between KAF156 and LUM-SDF combo and Coartem® in PCR-corrected ACPR at Day 29 is the primary efficacy endpoint (see [Section 12.4](#)).

### PCR-corrected ACPR and uncorrected ACPR:

At each visit, the percent of patients with ACPR with 95% confidence intervals will be provided using Clopper-Pearson method for each treatment group and Cohort. For exploratory purpose, 2-sided 95% confidence intervals for the difference at each visit between the 2 treatment groups will be constructed for each Cohort using the Wilson uncorrected method. For the Cohorts 1 and 2 pooled, the treatment difference and 95% CI between KAF156 and LUM-SDF and Coartem® will be evaluated using a Mantel-Haenszel estimate of the common risk difference stratified by cohort (see [SAS manual version 13.2 Pages 2681-2682, 2014](#)).

Data will be handled as follows:

- Treatment failures after 7 days (i.e., Day 8) due to new infection (ie, reinfection) based on PCR genotyping are not considered as failure for PCR-corrected analyses.
- For parasitological uncorrected ACPR, patients will be considered as failure on and after the visit when a new infection with *P. falciparum* is detected
- Patients who received rescue medication for the treatment of *P. falciparum* malaria (except for the treatment of a new infection) will be considered treatment failures (from the day of rescue use onwards). Patients who received other concomitant medication having an effect on malaria for reasons other than rescue therapy, e.g. for the treatment of *P. vivax* [REDACTED] (e.g. primaquine, certain antibiotics (sulfonamides, tetracycline, etc.)) will be considered in the analysis as if they had not taken the drug.
- Patients will be counted as failure at a visit (e.g., Day 15, etc.) if (a) they did not have a parasite count at that visit unless these patients could be classified as cured based on absence of parasitaemia at a later time (e.g., Day 29), or (b) they did not have valid PCR evaluations at baseline and the visit if parasitaemia was present at that time (e.g., Visit Day 15).

In addition, PCR-corrected ACPR rate will be calculated and plotted using the Kaplan-Meier method for each treatment group in the FAS (see [Section 12.4.4](#)).

Patients tested positive to COVID-19 after a visit or after *P. falciparum* re-appearance (recrudescence or new infection) are included in analysis similarly to other patients. Patients tested positive to COVID-19 prior to a visit without *P. falciparum* re-appearance are handled similarly to other patients with missing visit assessment. If there are significant number of patients tested positive to COVID-19 prior to a visit without *P. falciparum* re-appearance, additional sensitivity analyses may be considered.

### **Treatment failure related parameters:**

For the following parameters, 2-sided 95% confidence intervals will be provided for each treatment group using the Clopper-Pearson method by cohort and for Cohorts 1 and 2 pooled:

- proportion of patients with ETF
- proportion of patients with LCF
- proportion of patients with LPF

In addition, following analysis will be performed. 2-sided 95% confidence intervals for the difference between KAF156 and LUM-SDF combo and Coartem® will be provided for Cohorts 1 and 2 pooled using a Mantel-Haenszel estimate of the common risk difference stratified by cohort. 2-sided 95% confidence intervals for the difference between the 2 treatment groups for each Cohort will be constructed using the Wilson uncorrected method.

The above parameters will be determined using the uncorrected parasite counts. In addition, patients whose outcome status cannot be determined due to incomplete/missing data will be excluded from analysis.

At each visit, PCR uncorrected failure will be classified into initial infection not cleared, ETF, LCF before Day 8, recrudescence, new infection, negative PCR, missing PCR, or missing assessment. The reason will be tabulated using the FAS.

### **PCT and FCT:**

Descriptive statistics (mean, standard error, median, quartiles) will be presented using the Kaplan-Meier method. Kaplan-Meier curves will be provided.

PCT will be calculated based on uncorrected parasite counts. Patients without parasite clearance for whatever reason will be censored at the time of last parasite assessment. Patients who were enrolled on the basis of history of fever and did not subsequently have a fever at pre-dose will not be included in the analysis of FCT. Patients without fever clearance for whatever reason will be censored at the time of last temperature assessment.

For Cohorts 1 and 2 pooled, the treatment difference between KAF156 and LUM-SDF and Coartem® will be evaluated at the 2-sided 5% significance level using a log-rank test stratified by cohort. For each cohort, the treatment difference between 2 treatment groups will be evaluated at the 2-sided 5% significance level using a log-rank test.

### **Recrudescence and reinfection:**

Reinfection is defined as appearance of asexual parasites after clearance of initial infection with a genotype different from those parasites present at baseline. Reinfection must be confirmed by PCR analysis.

Recrudescence is defined as appearance of asexual parasites after clearance of initial infection with a genotype identical to that of parasites present at baseline. Recrudescence must be confirmed by PCR analysis.

Incidence rates of recrudescence and reinfection at Days 15, 29 and 43 will be estimated by Kaplan-Meier method based on the subset of FAS patients who have clearance of initial

infection by Day 7. Time to event (recrudescence or reinfection) will be calculated from the time of first study medication to the date of first event if a patient experiences the event and be censored at the time of last parasite assessment if a patient does not experience the event due to whatever reason.

For Cohorts 1 and 2 pooled, the treatment difference between KAF156 and LUM-SDF and Coartem® will be evaluated at the 2-sided 5% significance level using a log-rank test stratified by cohort. For each cohort, the treatment difference between 2 treatment groups will be evaluated at the 2-sided 5% significance level using a log-rank test.

### **12.5.2 Safety endpoints**

For all safety analyses, the safety set will be used. All listings and tables will be presented by cohort and treatment group.

Safety summaries (tables, figures) include all post treatment data with the exception of baseline data which will also be summarized where appropriate (e.g. change from baseline summaries). In particular, summary tables for adverse events (AEs) will summarize using all post-treatment events, with a start date on or after the first treatment (treatment-emergent AEs).

#### **Adverse events:**

All information obtained on adverse events will be displayed by cohort, treatment group, and patients.

The number (and percentage) of patients with treatment emergent adverse events (events started after the first dose of study medication or events present prior to start of study treatment but increased in severity based on preferred term) will be summarized in the following ways:

- By cohort, treatment, primary system organ class and preferred term.
- By cohort, treatment, primary system organ class, preferred term and maximum severity.
- By cohort, treatment, Standardized MedDRA Query (SMQ) and preferred term.

[figure not shown]
Separate summaries will be provided for study medication related adverse events, death, serious adverse events, other significant adverse events leading to discontinuation, and adverse events leading to dose adjustment if there are enough events.

The number (and proportion) of patients with adverse events of special interest/related to identified and potential risks will be summarized by cohort and treatment.

A patient with multiple adverse events within a primary system organ class is only counted once towards the total of the primary system organ class.

#### **Vital signs:**

All vital signs data will be listed by cohort, treatment group, patient, and visit/time and if ranges are available, abnormalities (and relevant orthostatic changes) will be flagged. Summary statistics will be provided by cohort, treatment group, and visit/time.

## **12-lead ECG:**

PR, QRS, QT, QTcF, QTcB, and RR intervals will be obtained from 12-lead ECGs for each patient during the study. ECG data will be read and interpreted (centrally).

Categorical Analysis of QT/QTc interval data based on the number of patients meeting or exceeding predefined limits in terms of absolute QT/QTc intervals or changes from baseline will be presented. In addition, a listing of these patients will be produced (by cohort and treatment group). Post treatment max QTc increase from baseline will be calculated for each patient and 2-sided confidence intervals for the difference between the 2 treatment groups will be calculated using the 80% confidence level for Run-in Cohort and the first 24 patients in Cohort 2 for Data Review checks and the 90% confidence level for all patients in each cohort at the final analysis.

All ECG data will be listed by cohort, treatment group, patient and visit/time, abnormalities will be flagged. Summary statistics will be provided by cohort, treatment group, and visit/time.

## **Clinical laboratory evaluations:**

All laboratory data will be listed by cohort, treatment group, patient, and visit/time and if normal ranges are available abnormalities will be flagged. Summary statistics will be provided by cohort, treatment group, and visit/time. Shift tables using the low/normal/high/ (low and high) classification will be used to compare baseline to the worst post-treatment value.

[figure not shown]
### **12.5.3 Pharmacokinetics**

Plasma concentration data will be listed by cohort, treatment group, patient, and visit/sampling time point. Descriptive summary statistics will be provided by cohort, treatment group, and visit/sampling time point, including the frequency (n, %) of concentrations below the LLOQ and reported as zero.

Summary statistics will include mean (arithmetic and geometric), SD, CV (arithmetic and geometric), median, minimum, and maximum. Concentrations below LLOQ will be treated as zero in summary statistics and for PK parameter calculations. For geometric related mean and CV, concentrations below LLOQ will be included as half of the LLOQ value.

Pharmacokinetic parameters will be listed by cohort, treatment group, and patient. Descriptive summary statistics will include mean (arithmetic and geometric), SD, and CV (arithmetic and geometric), median, minimum, and maximum. An exception to this is  $T_{max}$  where median, minimum, and maximum will be presented.

Two-sided 90% confidence intervals for AUC, Cmax and Tmax PK parameters and C168 of KAF156 and lumefantrine will be calculated by cohort and treatment group using normal or log-normal approximation as applicable. For relevant common PK parameters (related to KAF156 and lumefantrine for Run-in cohort and related to lumefantrine for Cohorts 1 and 2), two-sided 90% confidence intervals for geometric mean ratio between the 2 treatment groups will be provided by cohort.

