Malaria blood film for asexual parasite counts	X		X					X		X	X							X	X	X
Adverse events			X																	
Contact IRT	X		X								X									
Informed consent		X																		
Inclusion / Exclusion criteria		X																		
Medical history/current medical conditions		X																		
Prior and concomitant medications		X	X								X								X	X
Signs and symptoms of severe malaria		S	S								S								S	S
Physical Examination		S	S								S								S	S
Blood Pressure		X	X								X								X	X
Body Temperature 		X	X								X					X		X	X	X

Period	Screening		Treatment																	Follow-up	
Visit Name	Pre-Screening	Screening	Day 1									Day 2								Day 3	Day 4
Days	-1	-1	1									2								3	4
Time (post-dose)	-	-	0h	1h	3h	4h	5h	6h	8h	12h	24h	25h	27h	28h	29h	30h	32h	36h	48h	72h	
Body Height		X																			
Pulse rate		X	X								X								X	X	
Body Weight		X	X								X										
Clinical Chemistry		X									X								X		
Hematology		X									X								X		
Thyroid function		X																			
Urinalysis		X									X								X		
Pregnancy test (Run-in Cohort only) 		X																			
Blood sampling for parasite PCR genotyping 		X									X								X	X	
Drug administration record			X								X										
Meal record			X									X									
PK sampling for Run-in Cohort 		X		X	X	X	X	X	X		X 	X	X	X	X	X	X		X	X	
Electrocardiogram (ECG)		X			X			X			X		X			X			X	X	
Overnight Hospital Stay		S	S									S								S	

Period	Follow-up					UNS
Visit Name	Day 5	Day 8	Day 15	Day 29	Day 43 / EOS	UNS
Days	5	8	15	29	43	1 to 43
Time (post-dose)	96h	168h	336h	672h	1008h	-
Pre-screening Informed Consent						
Pre-screening Inclusion criteria						
Demography						
Malaria blood film for asexual parasite counts	X	X	X	X	X	X
Adverse events	X					
Contact IRT	X	X	X	X	X	
Informed consent						
Inclusion / Exclusion criteria						
Medical history/current medical conditions						
Prior and concomitant medications	X	X	X	X	X	X
Signs and symptoms of severe malaria	S	S	S	S	S	S
Physical Examination	S	S	S	S	S	
Blood Pressure	X	X	X	X	X	X
Body Temperature 	X	X	X	X	X	X
Body Height						
Pulse rate	X	X	X	X	X	X
Body Weight					X	X
Clinical Chemistry		X		X	X	X
Hematology		X		X	X	X
Thyroid function			X		X	
Urinalysis		X		X	X	X
Pregnancy test (Run-in Cohort only) 						
Blood sampling for parasite PCR genotyping 		X	X	X	X	X

Period	Follow-up					UNS

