**Table 12-1 Non-compartmental pharmacokinetic parameters**

AUC0-t	The AUC from time zero to time t (e.g. 24h) (µg•h/mL)
Cmax	The maximum (peak) observed plasma drug concentration (ng/mL)
Tmax	The time to reach maximum (peak) plasma, blood, serum, or other body fluid drug concentration after last dose administration (time)
C168	The observed plasma drug concentration at scheduled time point of 168 h post first dose administration (ng/mL)

In addition, the collected data may be analyzed by population PK modeling approach either for this study specifically or after pooling the data with other studies; the broad principles outlined in the Food and Drug Administration (FDA) Guidance for Industry: Population Pharmacokinetics would be followed. The Population PK modeling may not be part of the clinical study report and will be reported separately.

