2.9 Pharmacokinetic endpoints

The PK objectives are to assess PK parameters of KAF156 and lumefantrine in fasted or fed pediatric patients and to investigate the effect of food on lumefantrine PK and KAF156 PK in a Run-in Cohort of patients 12 to <18 years old.

PK parameters such as AUC_{inf}, AUC_{last}, AUC_{0-t}, C_{168h}, C_{max} and T_{max} (if feasible), will be used to evaluate these objectives, if available.

PK concentrations below the limit of quantification will be treated as zero in summary statistics and for the calculation of pharmacokinetic parameters by non-compartmental analysis. Descriptive statistics of pharmacokinetic parameters will include arithmetic and geometric means, standard deviation (SD), coefficient of variation, (CV %), median, minimum, and maximum, etc. CV% geo-mean will be calculated using this formula; $(\sqrt{\exp(\text{variance for log transformed data}) - 1}) * 100$.

In the study, rich PK data will be collected from the Run-in Cohort whereas Cohort 1 and 2 will provide sparse PK samples. A separate PK analysis will be performed for each Cohort.

Parameters will be reported for the Run-in Cohort using non-compartmental method of analysis (using Phoenix 6.4 or higher).

Two-sided 90% confidence intervals for AUC, C_{max} and T_{max} PK parameters of KAF156 and LUM-SDF will be calculated by cohort, day and treatment group using normal or log-normal approximation as applicable. Non-compartmental PK analysis for patients with sparse data will also be conducted and feasible PK parameters will be reported. Two-sided 90% confidence intervals for geometric mean ratio for KAF156 and LUM-SDF between fed vs fasted will be provided for Run-in cohort

A descriptive statistic for concentration at all nominal time points including 168 hours post dose would also be reported for all the patients.

PK parameters/ PK concentration will also be explored graphically. PK parameters/ PK concentration in Cohorts 1 and 2 will be summarized by age subgroup and body weight subgroup as per section 2.3.

PK data may be pooled for population pharmacokinetics analysis and the broad principles outlined in the Food and Drug Administration (FDA) Guidance for Industry: Population Pharmacokinetics would be followed. Additionally, PK exposure from the first few patients in each treatment group may be compared across the treatment groups and with the historical data to ensure that exposures are within the acceptable safety and efficacy.

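### Tmax is limited to median, minimum and maximum, yet both documents ask for a normal or log-normal 90% CI for it; that interval can under-cover and is uninformative where one plausible sample follows the dose

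*Protocol*

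**What the plan says.** Protocol 12.5.3 lists means, SD and CV for PK parameters and makes Tmax an exception, "where median, minimum, and maximum will be presented". The following paragraph nevertheless states: "Two-sided 90% confidence intervals for AUC, C max and T max PK parameters and C 168 of KAF156 and lumefantrine will be calculated by cohort". The method named there is a normal or log-normal approximation within each treatment group. The protocol also plans a geometric mean ratio between the two treatment groups for relevant common PK parameters. Table 12-1 counts Tmax to the peak "body fluid drug concentration after last dose administration (time").

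SAP 2.9 includes Tmax in a list qualified by feasibility. It gives means, SD and CV for PK parameters with no Tmax exception, and asks for 90% intervals for AUC, Cmax and Tmax "of KAF156 and LUM-SDF will be calculated by cohort, day and treatment group using normal or log-normal approximation as applicable". The fed versus fasted contrast is again a geometric mean ratio.

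Tmax is a named endpoint for the Run-in food effect, for both drugs, and for PK in Cohorts 1 and 2 (Protocol Table 2-1; SAP Table 1-2).

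**The concern.** A normal or log-normal interval is built from a mean and SD on the raw or log scale. The protocol excludes both for Tmax one paragraph before it asks for the interval. The SAP repeats the interval and is silent on the exception, so the two instructions pull in different directions.

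Tmax is also tied to the sampling schedule and takes few values. A single late peak can dominate the mean and SD of a small group. Where only one sample can plausibly hold the peak, the interval looks precise because of the design, not because of the drug. At stake is the reported uncertainty of a secondary endpoint with about 9 to 10 evaluable patients per Run-in group.

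**Working it through.** **1. Group size.** The plan states no figure for Tmax, so I first reproduced the Run-in precision statement that supplies n (Protocol 12.8.2; SAP 3.1.2). The probability that the 90% half-width for a difference of log means is at most 0.693 is P[χ²(2n−2) ≤ (2n−2)(s\*/SD)²], with s\* = 0.693 / (t(0.95, 2n−2) × √(2/n)).

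- n = 8, SD 0.69: s\* = 0.693/(1.761 × 0.5) = 0.787, P = 80.3% (plan: 80%).
- n = 9, SD 0.69: P = 90.7% (plan: 90%).
- n = 10, SD 0.77: P = 85.3% (plan: 80%; n = 9 gives 73.8%, so 10 is the smallest adequate n).

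Twelve per group less 20% gives 12 × 0.8 = 9.6, matching the stated 9 to 10.

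**2. Possible Tmax values in the Run-in.** Protocol Table 8-1 ("PK sampling for Run-in Cohort") has samples after the 24 h dose at 25, 27, 28, 29, 30, 32, 48, 72 and 168 h. Subtracting 24 h gives 1, 3, 4, 5, 6, 8, 24, 48 and 144 h: nine nominal values, six of them within 8 h.

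**3. Coverage of a nominal 90% interval.** The documents give no Tmax distribution, so every case below is assumed (n = 9, 10 and 12; 200,000 samples each; t quantiles).

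| Assumed Tmax distribution | Raw scale | Log scale |
|---|---|---|
| Peaks spread over 3 to 8 h | 88.5-89.1% | 89.4-90.1% |
| Log-normal, CV 30-50%, moved to the grid | 88.3-89.6% | 89.6-90.7% |
| 5% of patients peak at 24 h | 67.5-69.5% | 90.1-90.8% |
| 10% of patients peak at 24 h | 62.8-71.2% | 82.6-83.6% |
| 20-30% of patients peak at 24 h | 85-92% | 86-91% |
| 95% of patients share one time | 37-46% | 37-46% |

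The 10% row has a simple cause. With n = 10, a share 0.9¹⁰ = 34.9% of samples contains no late peak. The other patients average (7.15 − 0.1 × 24)/0.9 = 5.28 h against a true mean of 7.15 h. The simulated miss rate at n = 10 is 34.3% (coverage 65.7%), about that same share.

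In the last row all patients share the common time with probability 0.95⁹ = 63% (n = 9) to 0.95¹² = 54% (n = 12), and the interval then has zero width.

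A z quantile in place of t covers only 86.1-87.2% at n = 9 to 12 even for normal data.

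**4. Coartem arm.** The last dose is at 60 h (Protocol 6.7.2). Table 8-2 samples at 24 and 48 h (both pre-dose), 68 h and 168 h. After the last dose Tmax can nominally be 68 − 60 = 8 h or 168 − 60 = 108 h.

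- Nominal times, all peaks at 68 h: SD = 0, width = 0.
- Actual times, with uniform scatter over the ±2 h window (assumed): SD = 2/√3 = 1.155 h. The half-width is 1.796 × 1.155/√12 = 0.60 h for n = 12, or 1.667 × 1.155/√70 = 0.23 h for n = 70. Both reflect collection scatter only.
- If 1% of children peak at 168 h (assumed), the chance that all share 8 h is 0.99¹² = 89% or 0.99⁷⁰ = 50%.

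**5. Day 1 under the 3-day regimen.** SAP 2.9 asks for intervals by day. In Protocol Table 8-3, children under 6 years on KAF156/LUM-SDF have their first sample at 24 h, before the second dose. A Day 1 Tmax can then only be that sample. The SAP 2.2 food-compliance sets for Cohorts 1 and 2 refer to three dosing days, which suggests that this schedule applies.

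**The case against.** The strongest reply is that this is two adjacent sentences about descriptive output that need reconciling. A reader might infer more, and three such inferences do not hold.

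- **That the Run-in intervals under-cover in general.** The grid alone costs almost nothing. The low figures need an assumed late-peaking minority or near-ties, and with 20-30% late peaks coverage largely recovers. Both documents leave the scale open, and the log scale holds about 90% with 5% late peaks.
- **That the Coartem interval will have zero width.** That needs nominal times and no peak at 168 h, and neither document says which times Tmax uses. The feasibility wording in SAP 2.9, and its naming of LUM-SDF rather than lumefantrine, may mean that no Coartem interval is produced. The protocol sentence, which names lumefantrine, could still reach that arm.
- **That the SAP withdraws the exception, or that the food effect on Tmax has no valid estimate.** SAP 2.1 refers back to protocol section 12, and SAP section 4 records no changes. Medians and ranges by group, with individual listings, are planned under the protocol.

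The consequence is also small. The key Run-in variables are Cmax, AUC0-24h and the 168 h concentration (Protocol 12.8.2). Changes to the food recommendation rest on lumefantrine Cmax (Protocol 6.7.2).

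All of this limits the size of the point. The conflict between the two instructions remains, as does the lack of information where one plausible sample follows the dose. The only planned fed-fasted PK contrast is a geometric mean ratio, which does not suit Tmax.

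**Conclusion.** The point holds in a limited form. Both documents request a normal or log-normal 90% interval for a variable that the protocol restricts to median, minimum and maximum. In the Run-in that interval can under-cover: about 63-71% on the raw scale with 5-10% of patients peaking at 24 h, and about 83% on the log scale with 10%, against 88-91% with no late peaks. These figures rest on assumed distributions and n of about 10; they show what can happen, not what will.

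For Coartem after 60 h, and for a Day 1 Tmax in children under 6 years on the 3-day regimen, the interval carries no information about the drug at either nominal or actual times. The Day 1 case arises from the SAP's by-day request, since Table 12-1 counts Tmax from the last dose.

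The primary analysis, the sample size and every decision rule are unaffected. This is worth correcting but minor.

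**What to change.** - Delete Tmax from the normal/log-normal CI sentence in Protocol 12.5.3 and SAP 2.9, and carry the median/minimum/maximum rule into SAP 2.9.
- For the Run-in food effect, report the Hodges-Lehmann fed-minus-fasted shift in Tmax with a rank-based, tie-aware CI at approximately 90%.
- State whether Tmax uses nominal or actual sampling times.
- Where only one plausible sample follows the dose, give counts per sampling time and no CI.

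The cost is minor rewording and one standard procedure; no new data are needed. The downside is a confidence level that is only approximately 90%, because of ties and small n. As an illustration of such steps, the order-statistic interval for a single-group median at n = 10 covers 89.1% (3rd to 8th value) or 97.9% (2nd to 9th).
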